5.1.1.1.4 Missing Data

General missing data handling conventions are specified for methodologies in Section 5.1.1.1.3 and summarized as follows:

Table 5–3	Missing Data Handling by Endpoint Type

Timing	Missing Data Handling
Treatment Period	 Responder rate: All participants included GLMM: If missing according to the line handling if
	 If missing covariates (including baseline if applicable) or missing values at all postbaseline analysis visits: Participant excluded If ≥1 non-missing value at any postbaseline analysis visit: Participant included
Treatment Period	 If missing covariates (including baseline if applicable) Participant excluded
Treatment Period	 If missing covariates (including baseline if applicable) or missing values at all postbaseline analysis visits Participant excluded If ≥1 non-missing value at any postbaseline analysis visit: Participant included
Treatment Period	 Missing at random assumed Sensitivity analysis for the primary efficacy endpoint to assess the robustness of the primary MMRM analysis to possible violation of the missing-at-random (MAR) assumption. A pattern-mixture model approach based on the "copy reference" method (Carpenter et al, 2013) will be used for
	Timing Treatment Period Treatment Period Treatment Period Treatment Period

CFB = change from baseline; ANCOVA = analysis of covariance;

MMRM = mixed model for repeated measures; GLMM = generalized linear mixed model.

5.1.1.2 Demographics

5.1.1.2.1 Analysis Populations

The distribution of participants within the analysis populations will be summarized as follows:

Table 5–4	Analysis Population	Summaries
-----------	---------------------	-----------

Population	Description	Timing	Methodology
ITT, mITT, and Safety	Distribution in total and by treatment	_	Categorical counts
populations	group		

5.1.1.2.2 Participant Disposition

Participant disposition encompasses the distribution of participants who complete, and discontinue each specified analysis period, along with eCRF-reported discontinuation reasons from each respective analysis period. Participant disposition will be summarized as follows:

Table 5–5Participant Disposition Summaries

Parameter	Description	Timing	Methodology
Screening disposition ¹	Number of screened participants in total	Screening Period	Categorical
			descriptives
Treatment Period	Distribution in the ITT Population in total	Treatment Period	Categorical

Parameter	Description	Timing	Methodology
disposition ¹	and by treatment group		descriptives
Follow-up period	Distribution in the ITT Population in total	Safety Follow-up	Categorical
disposition ¹ and by treatment group Period descriptives			
¹ Participant disposition will be listed and participants who prematurely discontinued will be listed.			

5.1.1.2.3 **Protocol Deviations**

Protocol deviations will be defined in Protocol Deviation Requirement Specification, including importance classification. Protocol deviations will be summarized as follows:

Parameter	Description	Timing	Methodology
Major protocol	Distribution in the ITT Population in total	_	Categorical
deviations ¹	and by treatment group		descriptives
1			

¹ Protocol deviations will be listed.

5.1.1.2.4 Demographics

Demographics will be summarized by treatment group for the Safety and mITT populations, as follows:

Table 5–7	Demographic Summaries

Parameter	Description	Timing	Methodology
Age ¹	Age (years) relative to informed consent date	Informed consent	Continuous descriptives
Age group	• <20 • $20 - 29$ • $30 - 39$ • $40 - 49$ • $50 - 59$ • $60 - 69$ • $>=70$	Informed consent	Categorical descriptives
Sex, race, and ethnicity ¹	 eCRF categories Race group White Non-white 	Screening Period	Categorical descriptives

¹ Participant demographics will be listed.

5.1.1.2.5 Baseline Characteristics

Baseline characteristics will be summarized in total and by treatment group for the Safety and *m*ITT populations as follows:

Table 5–8Baseline Characteristics Summaries

Parameter	Description	Timing	Methodology
Baseline characteristics ¹	• Height (m)	Latest assessment in	Continuous
		Screening Period	descriptives

Parameter	Description	Timing	Methodology
	 Weight (kg) Body mass index (BMI) 		
	• Weight (kg) / height (m) ²		
Baseline efficacy	 Endpoints and timing fully described in Section 5.1.1.3 Number of MPM headache days Number of headache days Number of acute medication use days 	The first 28 days of the screening period, starting with the day of the screening visit	Continuous descriptives

¹ Participant baseline characteristics will be listed.

MPM = migraine/probable migraine.

5.1.1.2.6 Medical History

Medical history, encompassing abnormalities and surgeries reported as occurring before the Screening Visit, will be coded using the Medical Dictionary for Regulatory Activities (MedDRA), version 19.0 or newer. Unique participants who report medical history events will be summarized by MedDRA system organ class (SOC) and preferred term (PT) in total and by treatment group for the Safety Population as follows:

Table 5–9	Medical]	History	Summarv
			~~~~~

Parameter	Description	Timing	Methodology
Medical history ¹	Abnormalities and surgeries occurring	Screening Period	Categorical
	before the Screening Visit		descriptives

SOCs will be sorted alphabetically; PTs will be sorted in descending frequency in the highest dose group. ¹Participant medical history will be listed.

#### 5.1.1.2.7 Migraine History

Migraine history, including diagnosis, duration of disorder, previous use of prophylaxis treatment, average frequency of migraines or headache days per month in past 3 months, and acute treatments will be reported in total and by treatment group for the Safety Population as follows:

Table 5–10Medical History Summary

Parameter	Description	Timing	Methodology
Migraine Diagnosis ¹	With Aura, Without Aura, Both	Screening Period	Categorical
			descriptives
Duration of migraine ¹	In the Table summarize in Years,	Screening Period	Continuous
	in the Listing show original data		descriptives
	in Years and Months		
Previous Prophylaxis Migraine	Yes or No	Screening Period	Categorical
Treatment ¹			descriptives
Average number of migraine days		Screening Period	Continuous
per month in the last 3 months ¹			descriptives
Average number of headache days		Screening Period	Continuous
per month in the last 3 months ¹			descriptives

Table 5–11

Parameter	Description	Timing	Methodology
Acute Migraine Treatment ¹	Categorize as Yes or No, and subcategorize the Yes by: Triptan Ergot or ergot combinations NSAID Opiate or opiate combination Antiemetic agent	Screening Period	Categorical descriptives
	

Barbituates

Other

		

¹Participant migraine history will be listed.

#### 5.1.1.2.8 Prior and Concomitant Medications

**Medication Summaries** 

Medications will be coded using the World Health Organization (WHO) Drug Dictionary Enhanced (DDE), version MAR2016 or newer. Unique participants who reported medications will be summarized by Anatomical Therapeutic Chemical (ATC) 4 class and PT in total and by treatment group for the Safety Population as follows:

Parameter	Description	Timing	Methodology
Prior medications ¹	Medications taken $\geq 1$ time before the study treatment start date, regardless of medication end date	Screening Period	Categorical descriptives
Concomitant medications ¹	
 
Medications taken ≥ 1 time on or after the study treatment start date, regardless of medication start date
 
Medications starting 1 day after treatment end date will be listed but excluded from analysis
 
	Treatment Period	Categorical descriptives

ATC4 classes will be sorted alphabetically; PTs will be sorted in descending frequency in the highest dose group. ¹Participant prior and concomitant medication will be listed.

#### 5.1.1.3 Efficacy and Pharmacokinetic Analyses

Efficacy analyses will be based on the mITT Population.

The following efficacy assessments and terms are defined:

For analyses of headache characteristics and acute medication use, the first 28 days of the screening period, starting with the day of the screening visit, will serve as the "baseline". Baseline assessments for applicable efficacy endpoints defined as follows:

Table 5–13Efficacy Endpoint Baseline Definitions			
Endpoint	Description	Timing	
Baseline number of MPM headache days	The total number of reported MPM headache days divided by the total number of days with non-missing eDiary records during the 4-week baseline period and multiplied by 28. Refer to Section 6.4.1 for details.	The first 28 days from screening visit to the day before randomization	
Baseline number of headache days	The total number of reported headache days divided by the total number of days with non- missing eDiary records during the 4-week baseline period and multiplied by 28. Refer to Section 6.4.1 for details.	The first 28 days from screening visit to the day before randomization	
Baseline average headache day pain intensity	Baseline average headache day pain intensity is calculated for days with non-missing eDiary data during baseline period. Refer to Section 6.4.1 for details.	The first 28 days from screening visit to the day before randomization	
Baseline cumulative headache hours	Average daily headache hours are calculated for days with non-missing eDiary data during baseline period. Baseline cumulative headache hours are calculated as average daily headache hours multiplied by 28. Refer to Section 6.4.1 for details.	The first 28 days from screening visit to the day before randomization	
Baseline number of acute medication use days	The total number of reported acute medication use days divided by the total number of days with non-missing eDiary records during the 4- week baseline period and multiplied by 28. Refer to Section 6.4.1 for details.	The first 28 days from screening visit to the day before randomization	
Baseline number of triptan use days	The total number of reported triptan use days divided by the total number of days with non- missing eDiary records during the 4-week baseline period and multiplied by 28. Refer to Section 6.4.1 for details.	The first 28 days from screening visit to the day before randomization	

MPM = migraine/probable migraine.

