7.1 Analysis Populations

All safety analyses will be performed using the safety population, consisting of all patients who received at least one dose of the study treatment. For safety data analyses, the patients will be analyzed according to actual treatment received (rather than as randomized). The Intent-to-Treat (ITT) Population will consist of all randomized patients. All efficacy analyses will be performed using the modified intent-to-treat (ITT) population, consisting of all

randomized patients who received at least 1 dose of study treatment, had an evaluable baseline period of diary data, and had at least 1 evaluable post-baseline 4-week (Weeks 1-4, 5-8, and 9-12) of diary data. For efficacy data analyses, the patients will be analyzed according to randomization assignment, regardless of actual treatment received.

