5.1.1.1 Common Conventions

5.1.1.1.1 Analysis Populations

The analysis populations will consist of participants as defined below:

Population Definition		Study Treatment
Screened	All screened participants who sign informed consent	—
Intent-to-Treat (ITT)	All randomized participants	Randomized assignment
Modified Intent-to- Treat (mITT)	 All randomized participants who received ≥ 1 dose of study treatment, had an evaluable baseline period of diary data, and had ≥ 1 evaluable post-baseline 4-week (Weeks 1-4, 5-8, and 9-12) of diary data For baseline, evaluable is defined as having at least 20 days of diary data during the 4-week baseline period For each post-baseline 4-week treatment period, evaluable is defined as having at least 12 days of diary data for that particular period 	Randomized assignment
Safety	ty All participants who received ≥ 1 dose of study treatment Actual received	

Table 5–1Analysis Populations

¹ Participants will be summarized according to the study treatment received for majority of treatment period.

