#### 6.4.3 Sensitivity Analysis

#### 6.4.3.1 Pattern-Mixture Model

The sensitivity analysis will use a pattern-mixture model (PMM) approach based on the *reference-based* copy reference method (Carpenter et al, 2013) for missing value imputation. *This approach considers a missing-not-at-random (MNAR) mechanism for missing data and is to assess the impact of potential deviation of MAR assumption in the primary analysis.* 

Note that the missingness is assumed monotonic. Any intermediate missing values, if any, will be imputed at first. If the intermediate missing value exists at the first postbaseline month, it is imputed using the average of baseline and next available postbaseline values; otherwise, intermediate missing values are imputed using last observation carried forward (LOCF) approach.

The details of missing data imputation using the copy reference method are as follows:

- 1. The reference-based approach uses the placebo group as the reference. The missing values in the reference group are imputed using the observed data in that group under the missing-at-random assumption. The missing pattern is defined by the participant's last visit with a non-missing value. The mean vector and the covariance matrix of the multivariate normal distribution are estimated for reference group.
- 2. For atogepant treatment groups, missing values are imputed based on the distribution estimated from the reference group (from Step 1).
- 3. The MI (Step 1 and 2) will be performed 20 times and result in 20 imputed datasets. Each of the 20 imputed datasets will be analyzed using ANCOVA model. For a given imputed dataset, the average change from baseline in monthly MPM headache days is calculated across the 3 post-baseline months and is used as the response variable in the model. The model includes treatment group as a fixed factor and baseline monthly MPM headache days as a covariate. The LS mean difference and corresponding SE is estimated from the model comparing each atogepant treatment group with the placebo group.
- 4. The ANCOVA analysis results from 20 completed datasets are combined for overall estimation and inference using Rubin's rule (1987) to produce a pooled estimate of LS mean difference, its SE, and corresponding p-value for the test of null hypothesis of no treatment effect.

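### The copy-reference sensitivity analysis is confined to mITT, so randomised patients with no evaluable postbaseline month enter no efficacy analysis and their effect cannot be shown

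*SAP*

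**What the plan says.** Protocol 7.1 defines an all-randomised set ("The Intent-to-Treat (ITT) Population will consist of all randomized patients") but places every efficacy analysis on the modified set. To be in that set a patient must have been randomised, received at least one dose, have an evaluable baseline, and have "had at least 1 evaluable post-baseline 4-week (Weeks 1-4, 5-8, and 9-12) of diary data". SAP Table 5-1 makes the last condition concrete: for a postbaseline period, "evaluable is defined as having at least 12 days of diary data for that particular period". SAP 5.1.1.3 repeats that "Efficacy analyses will be based on the mITT Population".

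SAP Table 5-14 lists the pattern-mixture model and robust regression as sensitivity analyses of the primary endpoint. SAP 6.4.3.1 says that the pattern-mixture approach "is to assess the impact of potential deviation of MAR assumption in the primary analysis". It names no population of its own. On patterns it says "The missing pattern is defined by the participant's last visit with a non-missing value", which leaves no pattern for a patient with no postbaseline value. SAP Table 5-3 likewise drops from the repeated-measures models anyone missing at every postbaseline visit.

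In the text available, the ITT set serves only population counts, disposition and protocol deviations (SAP Tables 5-4 to 5-6).

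**The concern.** The mITT condition on postbaseline diary data is a selection made after randomisation. For the primary MMRM this costs little: a patient with no postbaseline response adds nothing to the likelihood of change given baseline, whether nominally included or not. The sensitivity analysis is different. Its purpose is to ask what happens if the unobserved outcomes do not behave as missing at random implies, and the patients with no observed outcome at all are removed before that question is asked. What remains to be imputed is the later or intermittent months of patients who already have at least one observed month.

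The protocol describes the trial as pivotal and intended to support registration (Protocol 1.2). Adverse events and lack of efficacy are among its listed reasons for discontinuation (Protocol 8.8), so early loss could be related to treatment. A statement that the primary result is robust to missing data would then rest on a set from which the patients with the most missing data have been removed.

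**Working it through.** **Which patients are covered.** Setting the sections side by side:

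| Patient | Primary MMRM | Copy-reference analysis | Robust regression |
|---|---|---|---|
| At least one window with 12 or more diary days | in | in; missing months imputed | in, if the analysis is triggered |
| Dosed, no window reaches 12 diary days | out | out | out |
| Randomised, never dosed | out | out | out |

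This follows from Protocol 7.1 and SAP 5.1.1.1.1, 5.1.1.3 and 6.4.3, which agree with one another.

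**Inputs.** Arm sizes, assumed differences and SD 3.0 come from Protocol 7.7 and SAP Table 5-25. Local alphas come from SAP 5.1.1.3.3: 0.025 for the two 60 mg regimens, 0.015 passed to the 30 mg regimens, and 0.01 for 10 mg QD once the four higher doses are rejected. The share d of an active arm with no evaluable postbaseline month is not given anywhere; 2% and 5% are assumptions.

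**Reproducing the plan's power.** With SE = 3.0 × sqrt(1/n + 1/180) and power = Φ(|δ|/SE − z for the two-sided local alpha):
- 60 mg BID: 97.1% (stated 97.0%).
- 60 mg QD: 99.4% (stated 99.3%).
- 30 mg BID: 92.5% (stated 91.4%).
- 30 mg QD: 97.7% (stated 98.1%).
- 10 mg QD: 69.9% at 0.01 and 80.4% at 0.025 (stated 80.3%), so the stated figure depends on recycled alpha.

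A 10,000-run simulation of the testing graph as the text describes it gives 97.1 / 91.1 / 99.3 / 97.7 / 80.1% (60 BID / 30 BID / 60 QD / 30 QD / 10 QD). It assumes secondary effects at 0.8 of the primary and a correlation of 0.6 between endpoints, because the documents give neither. The 10 mg QD result ranges from 69.0% to 85.0% as the secondary effect ratio goes from 0 to 1.0. The power table can stand as the starting point.

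**Effect on the estimate.** Under copy reference, an active-arm patient with only a baseline is imputed with the placebo mean given that baseline, so that patient's expected contribution to the difference is zero. The expected difference becomes δ × (1 − d):
- 60 mg QD, d = 2%: −1.50 × 0.98 = −1.470.
- 60 mg QD, d = 5%: −1.50 × 0.95 = −1.425.
- 10 mg QD, d = 2%: −1.20 × 0.98 = −1.176.
- 10 mg QD, d = 5%: −1.20 × 0.95 = −1.140.

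**Effect on z for 10 mg QD.** At full size, SE = 3.0 × sqrt(1/90 + 1/180) = 0.387 and z = 1.2/0.387 = 3.10. That is not the right comparator, because mITT is smaller. With the same loss d in both arms, the mITT z is 3.10 × sqrt(1 − d), and the all-randomised copy-reference z is 3.10 × (1 − d):

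| Assumed d | z on mITT | z with all imputed | Critical value, alpha 0.01 |
|---|---|---|---|
| 2% | 3.07 | 3.04 | 2.58 |
| 5% | 3.02 | 2.94 | 2.58 |

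The expected z would reach 2.58 only at d = 1 − 2.58/3.10 = 0.168, about 17% of the arm.

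These z values are approximations. They hold the SD at 3.0, ignore between-imputation variance, and set aside the dilution that later missing months already cause under copy reference.

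**The case against.** The case against has substance. Protocol and SAP agree on mITT, so nothing is contradictory, and the pattern-mixture analysis tests missing at random on the same population as the primary analysis, which is a defensible reading of its stated purpose. The exclusions are not concealed: SAP Table 5-4 gives ITT and mITT counts by arm, and SAP Table 5-5 gives discontinuation reasons by arm on ITT. A reader can therefore see how large the gap is. Those tables do not give the reason for exclusion from mITT, and they cannot show what the gap does to the estimate.

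Several stronger readings are tempting and are not supported:
- **That anyone who stops treatment in the first days is lost.** Protocol 6.6 plans diary use until Visit 8, Protocol 8.8 asks early discontinuers to attend the final visits, and SAP 6.2.1 sets windows by day from treatment start with no stated cut at last dose. A patient who stops on day 5 and keeps the diary can reach 12 days and remain in mITT. Protocol 7.2 and SAP 6.4.1 describe recording during the double-blind period, so use of entries made after stopping is not spelled out, but removal is not automatic.
- **That these are the most informative dropouts.** The documents give no count, timing or reasons for early loss, and the group also contains poor diary completers and patients never dosed.
- **That any imbalance between arms enlarges the shift.** Under copy reference the expected shift is δ × d with d the active-arm share. Placebo patients are imputed from placebo data, so excess placebo loss adds no expected shift.
- **That conclusions would change.** At the assumed rates, none of the expected z values above falls below its threshold.

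**Conclusion.** The point holds as a gap in coverage. No planned efficacy analysis, under any missing-data assumption, includes randomised patients without an evaluable postbaseline month, so the plan cannot demonstrate that their effect is small. It probably is small: at an assumed 2% to 5% of an active arm, the expected 60 mg QD difference moves by 0.03 to 0.075 days, and the 10 mg QD z by 0.03 to 0.08. These sizes rest on the assumed d, the planning differences and SD, and, for z, equal loss in the two arms being compared. The primary analysis, the alpha allocation and the power table are not in question. This is a worthwhile, inexpensive addition to make before database lock, not an error that undermines the trial.

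**What to change.** In SAP 6.4.3.1, state that the copy-reference analysis will additionally be run on all randomised patients with an evaluable baseline. Entry already requires at least 20 of 28 baseline diary days (Protocol 4.2), so this should leave out few patients. Add a missing-data pattern for patients with no postbaseline value, and impute all three months for them from the placebo distribution given baseline. The ANCOVA on the three-month average and the pooling by Rubin's rule then run unchanged. Extend SAP Table 5-4 to report exclusions from mITT by arm and by reason: never dosed, no evaluable baseline, no evaluable postbaseline window. Keep mITT for the primary MMRM.

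The cost is a short SAP addition, the same program run on a slightly larger dataset, and a sensitivity estimate that will be a little less favourable.

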#### 5.1.1.3.1 Efficacy Endpoints

The efficacy endpoints are summarized in the table below. Analyses of HEOR endpoints (ACM-I total and domain scores, PGIC, WPAI-SHP V2.0, *patient satisfaction with study medication, HIT-6,* and EQ-5D-5L) will be specified in a separate HEOR SAP.

Table 5–14Efficacy Analysis

Endpoint	Description	Timing	Methodology
Endpoint 1	Change from baseline in mean monthly MPM	Treatment	CFB MMRM
P1	headache days across the 12-week treatment period	period	Sensitivity Analyses:
			• PMM
			Robust regression

Endpoint	Description	Timing	Methodology
			(Refer to Section 6.4.3 for details)
Endpoint 2 S1	Change from baseline in mean monthly headache days across the 12-week treatment period	Treatment Period	CFB MMRM
Endpoint 3 S2	Proportion of participants with at least a 50% reduction in mean monthly MPM headache days across the 12-week treatment period	Treatment Period	Responder GLMM
Endpoint 4 S3	Change from baseline in mean monthly acute medication use days across the 12-week treatment period	Treatment Period	CFB MMRM

¹ Analysis visits defined in Section 6.2.1.

MPM = migraine/probable migraine. CFB = change from baseline; MMRM = mixed model for repeated measures; GLMM = generalized linear mixed model.

P1: primary efficacy parameter; S1-S3: secondary efficacy parameters. Endpoint 5 - 12: additional efficacy parameters

